#### Exclusion Criteria

Patients will be excluded if they: Experienced AKI within the previous three months, Are younger than 18 years, Have CKD stage 5, chronic dialysis, or kidney transplant, Had a hospital stay shorter than 48 hours, Have incomplete data preventing full análisis

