#### Secondary Objectives:

To evaluate the risk of rehospitalization, infection-related rehospitalization, septic shock, major adverse kidney events (MAKE) at 90 days, incidence of hyperkalemia, and new episodes of acute kidney injury. Adverse events (AEs) will be coded using the Medical Dictionary for Regulatory Activities (MedDRA) and classified as mild, moderate, or severe. AEs of special interest include skin rash, erythema, nausea, vomiting, headache, and tachycardia.

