#### Inclusion Criteria

Patients with severe AKI and known baseline serum creatinine (SCr) levels—defined as the most recent SCr value within the six months preceding hospitalization—will be included. Participants must also have available serum creatinine data for the months following discharge to assess major adverse kidney events (MAKE) at 90 days post-AKI.

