## Operationalization of Variables

### Independent Variable:

- Treatment: Administration of the study drug versus placebo (categorical variable with two levels: active treatment or placebo).

Dependent Variables (Primary Outcomes):

- Development of gastrointestinal infections — categorical nominal binary variable (yes/no)
- Development of upper respiratory infections — categorical nominal binary variable (yes/no)
- Development of lower respiratory infections — categorical nominal binary variable (yes/no)
- Development of urinary tract infections — categorical nominal binary variable (yes/no)
- Development of soft tissue infections — categorical nominal binary variable (yes/no)
- Rehospitalization due to infection — categorical nominal binary variable (yes/no)
- Development of septic shock — categorical nominal binary variable (yes/no)
- Requirement for long-term renal replacement therapy — categorical nominal binary variable (yes/no)
- Death from any cause — categorical nominal binary variable (yes/no)
- Progression to chronic kidney disease or  $\geq 50\%$  decline in eGFR — categorical nominal binary variable (yes/no)
- Worsening renal function with  $\geq 25\%$  decline in eGFR due to infection — categorical nominal binary variable (yes/no)
- Presence of hyperkalemia — categorical nominal binary variable (yes/no)
- Adverse drug reactions — categorical nominal variable

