## Data Collection and Observation Techniques

Data will be collected through automated extraction from the institutional electronic medical record system. Additional potential contributors to AKI—such as nephrotoxic medications (aminoglycosides, nonsteroidal anti-inflammatory drugs, and vancomycin)—will also be considered.

The presence of anaphylactic shock will be documented, and relevant biochemical parameters, such as serum iron levels and transferrin saturation, will be recorded for analysis.

Indications for renal replacement therapy (RRT) will include:

- Fluid overload refractory to diuretics
- Severe hyperkalemia
- Severe metabolic acidosis
- Uremic manifestations such as encephalopathy, pericarditis, or seizures

The study will be submitted to the Institutional Review Board (IRB) of the Hospital Civil de Guadalajara “Fray Antonio Alcalde” and registered at ClinicalTrials.gov with the corresponding registration number.

This research will adhere to the ethical principles outlined in the Declaration of Helsinki and will be designed in accordance with CONSORT (Consolidated Standards of Reporting Trials) guidelines.

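### No entry criterion concerns the study drug, so known hypersensitivity does not exclude a patient; separately, hyperkalemia is an incidence in the objectives but a presence in the variable list

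*Protocol*

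**What the plan says.** The protocol's entry rules are two short sections. Inclusion Criteria asks for "Patients with severe AKI and known baseline serum creatinine (SCr) levels", with creatinine data after discharge. Exclusion Criteria is a single list. It opens with recent AKI, continues "Are younger than 18 years, Have CKD stage 5, chronic dialysis, or kidney transplant, Had a hospital stay shorter than 48 hours", and closes with incomplete data. The list ends there.

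Drug-related safety appears elsewhere in the protocol:

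- Secondary Objectives: "AEs of special interest include skin rash, erythema, nausea, vomiting, headache, and tachycardia".
- Data Collection and Observation Techniques: "The presence of anaphylactic shock will be documented".
- Justification says, in general terms, that adverse events from antibiotic use matter for this trial and have to be addressed.
- Operationalization of Variables lists adverse drug reactions among the dependent variables.

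Hyperkalemia is described in two ways. Secondary Objectives refers to "incidence of hyperkalemia, and new episodes of acute kidney injury". Operationalization of Variables has a yes/no variable called "Presence of hyperkalemia".

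**The concern.** There are two separate problems.

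The first is eligibility. The protocol plans to watch for skin reactions and anaphylactic shock in patients given a sulfonamide combination, but no written rule keeps out a patient already known to react to it. Treatment is double-blind, so those assessing outcomes will not know that such a patient is on the active tablet. Screening is the point at which this avoidable exposure can be prevented, and it cannot be undone after randomisation.

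The second is an outcome definition. Incidence counts new events; presence counts anyone who has the condition. Patients enter soon after severe AKI, and Control Group Definition foresees kidney injury that is still recovering, so some may already be hyperkalemic at entry. If they score yes, they add the same background to both arms and make a true difference harder to see. For a safety outcome that is the wrong direction in which to err.

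**Working it through.** **Eligibility.** The protocol states no figure to reproduce, so the check is a reading of every section that could carry a drug-related entry rule.

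| Section | Content bearing on entry | Hypersensitivity or other drug-related rule? |
|---|---|---|
| Inclusion Criteria | severe AKI, known baseline creatinine, later creatinine data | no |
| Exclusion Criteria | recent AKI; age; CKD stage 5, dialysis or transplant; short stay; incomplete data | no (0 of 5) |
| Materials and Methods; Study Population | AKI patients under nephrology care | no |
| Sampling Method | records reviewed to confirm eligibility; study drug and placebo named | no |
| Control Group Definition | severe AKI resolved or recovering | no |
| Elimination Criteria | stopping the drug, non-infectious rehospitalization, dose deviation | acts only after treatment starts |

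The exclusion of CKD stage 5 and dialysis limits renal risk but is not framed as a drug criterion and says nothing about allergy. Elimination Criteria does not close the gap either: a patient who reacts and stops the tablets falls under elimination, so the reaction could leave the data set. That sits badly with the intention-to-treat statement in Statistical Analysis.

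**Hyperkalemia.** Let f be the share of patients hyperkalemic at entry, taken as equal in the two arms because of randomisation, and let p be the risk of new hyperkalemia among the rest. If entry cases score yes, then in each arm

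observed risk = f + (1 − f) × p.

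With p_A for active and p_P for placebo, the observed risk difference is (1 − f) × (p_A − p_P). It shrinks by the factor (1 − f). The observed risk ratio is [f + (1 − f) p_A] / [f + (1 − f) p_P], which lies nearer to 1 than p_A / p_P for any f above zero. The direction therefore does not depend on the values chosen.

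The documents give neither f nor p. The table is an illustration on assumed values, p_P = 5% and p_A = 15% (true difference 10.0 points, true ratio 3.0):

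| Assumed f | Placebo | Active | Difference | Ratio |
|---|---|---|---|---|
| 5% | 0.05 + 0.95 × 0.05 = 0.0975 | 0.05 + 0.95 × 0.15 = 0.1925 | 9.5 points | 1.97 |
| 10% | 0.10 + 0.90 × 0.05 = 0.1450 | 0.10 + 0.90 × 0.15 = 0.2350 | 9.0 points | 1.62 |
| 15% | 0.15 + 0.85 × 0.05 = 0.1925 | 0.15 + 0.85 × 0.15 = 0.2775 | 8.5 points | 1.44 |

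The same inputs look mild as a difference and severe as a ratio. Statistical Analysis plans a chi-square or Fisher test of proportions and names neither measure, so the table shows direction only.

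**The case against.** The strongest reply has four parts.

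*Investigators judge eligibility from the medical record, and an exclusion list does not oblige anyone to enrol.* This is fair. A reader might infer that a site must accept a known reactor, or that some calculable number of the 120 patients (2 × 60) will be hypersensitive. The documents support neither: enrolment is not compelled, and no prevalence is given. The written gap remains, because nothing requires such a patient to be kept out.

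*The protocol does not present all these events as harms expected from the drug.* This stands. Hyperkalemia and new AKI are secondary objectives, listed beside rehospitalization and septic shock, and are not attributed to the study drug. Anaphylactic shock is only to be recorded. The eligibility point therefore rests on rash and erythema, the recording of anaphylactic shock, and the general remark on antibiotic adverse events. That is enough for hypersensitivity.

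*A hyperkalemic patient need not be excluded.* This also stands. A reader might infer that a potassium criterion is missing by mistake. But scoring only new hyperkalemia removes the misclassification without any exclusion, and whether such patients should enter is a clinical decision. Contraindications from the product labelling would rest on a source outside the documents and form no part of this point.

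*Incidence, read with the 90-day observation window, already means new events, and an SAP may settle the baseline handling.* This is a reasonable reading, and it makes bias a possibility rather than a certainty. But the protocol's own variable is worded otherwise, and hyperkalemia present at discharge can still be present inside the window. The two sections should agree.

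**Conclusion.** The point holds in two limited parts.

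1. No entry rule is tied to the study drug, and a patient with known hypersensitivity to trimethoprim or sulfonamides is eligible as written. This rests on the text alone. Eligibility belongs in the protocol, so an SAP that is not shown would not be expected to supply it. Following the plan as written is worse for patient safety than the amended plan, so this is more than missing detail.

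2. The objective and the variable for hyperkalemia disagree. Read literally, the variable lets entry cases count in either arm and pulls the comparison toward no difference. The direction is certain if entry cases exist and are scored yes; the amount cannot be estimated from the documents.

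A reader might go further and conclude that the trial will substantially hide a hyperkalemia signal. The documents do not support that. On the illustrative inputs the difference falls only from 10.0 points to between 9.5 and 8.5, and the larger fall in the ratio comes entirely from assumed values.

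**What to change.** - **Exclusion Criteria:** add known hypersensitivity to a component of either study tablet. Either tablet is meant, because Sampling Method describes the placebo as a magnesium tablet.
- **Operationalization of Variables:** replace the hyperkalemia variable with new hyperkalemia after randomisation, so that it agrees with Secondary Objectives. State which potassium value counts as the entry value; the protocol describes no laboratory check before randomisation.
- **Eligibility and safety outcomes:** have the investigators reconcile the entry list with the safety outcomes that the protocol already names. Whether any potassium or other drug-related entry criterion is needed, and in what form, is for them to decide.

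The cost is a short amendment and the loss of a small share of screened patients. Sampling Method already has records reviewed for eligibility, so an allergy check fits that step. The protocol does not say whether allergy history and an entry potassium are routinely recorded; if they are not, a brief extra step at screening is needed.

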#### Elimination Criteria

- Patients who partially or completely discontinue the prophylactic antibiotic before completing three months of treatment
- Patients rehospitalized for non-infectious causes within the first three months
- Patients who take a different dose of prophylactic antibiotic than prescribed

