### Observation Unit

Patients diagnosed with severe AKI will be monitored for a period of 90 days after hospital discharge. Each participant will be evaluated based on infection incidence, rehospitalization, adverse events, and other health outcomes related to trimethoprim–sulfamethoxazole administration. Observation will focus on collecting clinical data and health outcomes specific to each participant.

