#### Sampling Method

Potential participants for this study will be identified during routine hospital rounds for patients with acute kidney injury (AKI) and through concurrent review of medical records to confirm eligibility. If a patient is deemed eligible, the principal investigator will contact them to explain the study and provide a participant information and consent form.

After discussion with the patient and family members, the nephrology staff will obtain written informed consent prior to any study-related evaluations.

The intervention drug will be trimethoprim–sulfamethoxazole 800/160 mg, administered under double-blind conditions. Blinding will be achieved by ensuring that participants do not witness preparation of the study medication, and by assigning unblinded study personnel—who will not participate in outcome assessments—to handle preparation and administration.

The placebo will consist of magnesium tablets, administered at the same frequency—one tablet every 48 hours for three months.

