#### Statistical Analysis

An intention-to-treat approach will be adopted, including all randomized participants who receive the intervention, for both primary and secondary outcomes.

Categorical variables will be expressed as counts and percentages (%) and compared using either the chi-square test or Fisher’s exact test, as appropriate.

Continuous variables will be reported as median values (IQR), since normal distribution is not expected according to the Shapiro–Wilk test; between-group comparisons will be performed using the Mann–Whitney U test.

A repeated-measures analysis of variance (ANOVA) will be used to compare variables over time between groups. A Kaplan–Meier survival curve will be plotted for both groups and compared using the log-rank test. Missing data will be imputed using the mean linear interpolation method.

All statistical tests will be two-tailed, and a p-value < 0.05 will be considered statistically significant.

The analyses and figures will be performed using MedCalc software (Version 22.0.21, Ostend, Belgium) and GraphPad Prism (Version 10.2.3, Boston, Massachusetts, USA).

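### Three post-randomisation elimination criteria contradict the stated intention-to-treat analysis, and the protocol does not say which rule governs

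*Protocol*

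**What the plan says.** The protocol's Elimination Criteria section, separate from its Exclusion Criteria, lists three groups:

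- The first concerns stopping the tablets early: "Patients who partially or completely discontinue the prophylactic antibiotic before completing three months of treatment".
- The second concerns a return to hospital for some other reason than infection: "Patients rehospitalized for non-infectious causes within the first three months".
- The third concerns departures from the planned regimen: "Patients who take a different dose of prophylactic antibiotic than prescribed".

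The Statistical Analysis section says: "An intention-to-treat approach will be adopted, including all randomized participants who receive the intervention". It applies this to primary and secondary outcomes alike. The Observation Unit section says: "Patients diagnosed with severe AKI will be monitored for a period of 90 days after hospital discharge". On what is to be assessed in that time, it adds: "Each participant will be evaluated based on infection incidence, rehospitalization, adverse events, and other health outcomes".

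Two other places bear on the point. Secondary Objectives lists all-cause and infection-related readmission as separate items: "To evaluate the risk of rehospitalization, infection-related rehospitalization, septic shock". Sampling Method describes a blinded comparator on the same schedule: "The placebo will consist of magnesium tablets, administered at the same frequency".

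The protocol does not say whether elimination ends treatment, follow-up or inclusion in the analysis. It names no per-protocol set and gives no order of precedence between these sections.

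**The concern.** A patient who stops tablets, takes them off schedule or is readmitted has already received the intervention. Even the protocol's modified form of intention-to-treat therefore keeps exactly the patients whom the Elimination Criteria remove. Both rules cannot hold for the same analysis.

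If the elimination rule decides who is analysed, several things follow:

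- **Selection on outcome or tolerance.** Tablets may be stopped because an infection is being treated or because of a drug reaction. This concerns mainly the first and third criteria. The second is not triggered by infection as worded, but it can follow from a renal event or an adverse effect.
- **A listed outcome collapses.** Once non-infectious readmissions are removed, all-cause readmission equals infection-related readmission among those retained.
- **Harms are undercounted in the comparison.** Reactions that lead to stopping drop out. Hyperkalaemia and new AKI are depleted, though not emptied, by the cases that lead to a non-infectious admission. Safety is a stated objective of this phase 2 trial.
- **Adherence cannot be assessed within the retained set**, although counts of eliminated patients would still show it.
- **Possible asymmetry.** Two of the criteria name only the antibiotic. This may be loose wording for study tablets, but read literally it acts on one arm.

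**Working it through.** **1. The texts side by side**

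| Event after treatment starts | Elimination Criteria | Statistical Analysis and Observation Unit |
|---|---|---|
| Stops tablets before three months | removed | retained, evaluated over 90 days |
| Non-infectious readmission | removed | retained; readmission is itself an outcome |
| Off-dose use | removed | retained |

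Neither of the sections in the last column makes an exception for these events. The contradiction needs no arithmetic.

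**2. The protocol's own sample size**

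Sample Size gives 59% v 29.5%, 95% confidence, 90% power and 60 per group. With the pooled variance in both terms:

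n = (1.960 + 1.282)² × 2 × 0.4425 × 0.5575 / 0.295² = 59.6, which rounds up to 60.

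The usual formula (pooled variance under the null, unpooled under the alternative) gives 58. The figure reproduces, with no allowance for eliminated patients. By the normal approximation, power is 91.2% with 60 per arm, 88.1% if 10% of each arm is lost at random and 84.0% if 20% is lost.

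**3. What selective elimination could do (assumed rates)**

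Let p be the true infection risk, and let qi and qu be the shares of infected and uninfected patients eliminated. Then

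retained risk = p(1 − qi) / [p(1 − qi) + (1 − p)(1 − qu)].

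For p = 0.30, qi = 0.25 and qu = 0.10: 0.225 / (0.225 + 0.630) = 26.3%.

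Rejection rates come from simulation: 60 per arm, uncorrected pooled two-proportion z-test at 1.96, 1,000,000 replicates per case. Rates are written qi/qu.

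*No true effect, 30% risk in both arms:*

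| Active | Control | Retained risk, active v control | Type I error |
|---|---|---|---|
| none | none | 30% v 30% | 5.2% |
| 25%/10% | 25%/10% | 26.3% v 26.3% | 5.1% |
| 30%/30% | 10%/10% | 30% v 30% | 5.1% |
| 25%/10% | 10%/10% | 26.3% v 30% | 7.2% |
| 10%/30% | 10%/10% | 35.5% v 30% | 9.2% (8.7% as apparent harm) |
| 50%/10% | 25%/10% | 19.2% v 26.3% | 13.2% (12.9% as apparent benefit) |

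On the literal active-arm-only reading, 25%/10% gives 7.2% and 50%/10% gives 24%.

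*True 59% v 29.5%, taking 59% as the control arm:*

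| Active | Control | Power |
|---|---|---|
| none | none | 92% |
| 25%/10% | 25%/10% | 85% |
| 50%/0% | 50%/0% | 76% |
| 10%/30% | 10%/10% | 68% |
| 24.1% at random | 10% at random | 85% |

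In the fourth row the active risk of 29.5% appears as 0.2655 / (0.2655 + 0.4935) = 35.0%, with on average 45.5 v 54.0 patients retained. The last row loses the same numbers at random. The gap, 0.851 − 0.675 = 0.176, is the part due to bias rather than to fewer patients.

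**The case against.** The strongest reply is that nothing here shows a planned biased analysis. The Elimination Criteria never say that these patients leave the analysis, and Statistical Analysis is the only section that defines an analysis population. Elimination might mean only the end of study participation, and a SAP that is not at hand might confine the criteria to a per-protocol set. This stands in part: the harm is conditional. It does not remove the contradiction, because the protocol states the criteria without limit and would need correcting even if a SAP resolved them.

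The numbers are also open to challenge, and fairly. Every elimination rate is assumed, and several plausible cases leave type I error near 5%. The protocol also allows Fisher's exact test, under which the 7.2% and 13.2% cases fall to about 5.6% and 10%. The 24% figure needs both the literal one-arm reading and a heavy loss of infected patients. Blinded staff could not apply a one-arm rule during the trial, so that case deserves little weight. The case for change rests on the text.

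Two further remarks are right but separate. Limiting intention-to-treat to those who receive treatment is already a modification. The eligibility requirements for complete data and post-discharge creatinine could also act after randomisation. Reconciling the elimination rule does not settle either.

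**Conclusion.** The concern holds. The protocol states two incompatible rules for who is analysed, and this is wrong as written rather than a detail left for a SAP. If Statistical Analysis and Observation Unit govern, these three events do not disturb the randomised comparison. If the Elimination Criteria govern, bias can run in either direction, and non-infectious readmissions and treatment-limiting harms drop out of the comparison.

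The size cannot be read from the protocol. Under the assumed rates, type I error ranges from about 5% (equal rates, or loss unrelated to infection) to 13.2% when the rule is applied to both arms. In the case where uninfected active patients are lost more often, power falls from 92% to 68%, of which about 18 points are bias. These figures rest on assumed rates, a 30% null risk, 59% as the control risk and an uncorrected z-test. The choice has to be settled before outcomes are known, since choosing afterwards could be driven by the result.

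**What to change.** State in both Elimination Criteria and Statistical Analysis: *Participants are followed to day 90 and analysed in the arm assigned, regardless of discontinuation, dose deviation or rehospitalisation.*

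Keep the three criteria only to define a labelled secondary per-protocol analysis, worded as study tablets and applied identically to both arms. Report the number meeting each criterion by arm, which also serves the adherence and safety objectives. No dose or treatment-stopping rule changes.

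The cost is protocol wording. Monitoring to 90 days is already planned and data come from the hospital's electronic record, so patients who stop tablets can be followed through the same source. That record covers one institution, so infections treated elsewhere may be missed. The statistical price is that non-adherence may dilute the estimated effect.
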